#### Handling missing data

##### Outcomes

When creating the composite measures for our behavior and attitude outcomes, we will create a composite score by taking the average of multiple individual items. For these measures, our current plan is to use 20% as a threshold for allowable missing items, based on guidance from evaluation technical assistance resources. This plan is contingent on the final distribution of missing data in our data set. If participants have more than 20% of items missing for a given construct, the respondent will be assigned a missing value for that construct and will be excluded from the analytic sample for that outcome. We will not be imputing truly missing values for outcomes. To create a construct score, the average will divide by the number of non-missing values in the construct.

Participants who have not seen their child within the past month will have their parenting behavior responses set to “Never” (1) and will be included in the analytic sample for that outcome.

Data for the implementation outcomes could be missing as a result of programmatic data entry issues. For the sake of this evaluation, we assume that any primary or support services received by a participant are being accurately logged into nFORM, so a lack of documented attendance, service contacts, referrals, etc. is indicative of lack of services (i.e., a participant not receiving the program components as intended).

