1. PROGRAM SUMMARY

Please provide a brief summary of your grant project including the needs to be addressed, the services provided, and the population served.

The Fresno region of California, at both the city and county levels, is a region impacted by high rates of poverty and unemployment. Prior research suggests that poverty is often inextricably linked to high crime rates. High crime rates can then lead to high rates of incarceration, thereby contributing to chronic father absenteeism and the breakdown of healthy families. The purpose of the Fresno Fatherhood program is to employ a comprehensive and holistic healthy marriage, responsible parenting and economic stability education and related services to at-risk adult community fathers (i.e., 18 and older) who have children aged 24 years or younger and reside in areas of high poverty. While the program does not plan on serving only fathers who are housed in treatment facilities, non-custodial, or justice involved, the grantee (FAWIC) expects that many will have these characteristics.

The core services of Fresno Fatherhood include: healthy marriage, responsible parenting, and economic stability education and services. These services will be delivered by using a primary workshop focused on fatherhood skills using the National Fatherhood Initiative's 24/7 Dad evidence-based/evidence-informed curricula; job readiness services, including career exploration and planning; job-driven employment services, including development of skills tied to demand jobs in growth sectors of the local economy; job placement assistance; intensive case management and service navigation support; mentoring to encourage and support fathers in applying the knowledge and skills they acquire through the project; supplemental workshops focused on life skills, financial literacy and personal development; and referrals to a full array of support services through both grant-funded and leveraged resources. FAWIC will provide parenting and relationship instruction via a primary workshop to 63 fathers in year 1 and 125 annually in years 2-5.

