### Defining analysis measures

For each outcome construct, we have identified the relevant measures from nFORM that are theoretically aligned with that construct. We will generate a correlation matrix between items in a given construct to ensure that theoretically related items are also empirically related in our data set. Items that are not strongly correlated with other items in a construct will be removed as necessary. Factor analysis will be used to ensure that all construct items hang together (using an alpha of 0.7 or higher as the threshold). If an alpha of 0.7 cannot be obtained, that outcome will be removed.

Once we are confident that all of the items align with a given construct, we will create a composite measure by taking an average of the scores on each non-missing item in the construct. The measure definition matrix below provides information on each proposed outcome. For composite measures, a change score will be calculated between a participant's pre-program composite score and post-program composite score. For standalone survey items, a change score will be calculated between a participant's pre-survey and post-survey responses.

For the sake of consistency and simplicity, parenting and co-parenting analyses will use a participant's youngest child as the focal child.

Measure	Sample	Variable Type	Data source(s)	Variable Name	Definition
Parenting attitudes	Has at least one child age 24 or younger, saw child within past month	Continuous (range from 1 to 5 where 1 is strongly disagree and 5 is strongly agree)	nFORM entrance, nFORM exit	Par_Att	Average of 7 survey items that relate to frequency of key parenting attitudes.

Parenting behaviors	Has at least one child age 24 or younger, saw child within past month	Continuous (range from 1 to 5 where 1 is never and 5 is every day or almost every day)	nFORM entrance, OLLE 1-year follow-up	Par_Beh	Average of 7 survey items that relate to frequency of positive interactions with participant's youngest child.
Co-parenting behaviors	Has at least one child age 24 or younger	Continuous (range from 1 to 5 where 1 is strongly disagree and 5 is strongly agree)	nFORM entrance, OLLE 1-year follow-up	Copar_Beh	Average of 11 survey items that relate to positive interactions with the mother of participant's youngest child.
Financial behaviors	Has at least one child age 24 or younger	Dichotomous (0/1)	nFORM entrance, OLLE 1-year follow-up	Fin_Beh	Binary measure of having opened a checking/savings account.

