#### **Analytic approach**

The main goal of this descriptive study is to assess pre-to-post change scores in the attitudinal outcomes listed above, and assess pre-to-one-year follow-up change scores in the behavioral outcomes listed above among program participants before and after primary workshops. We will use paired sample t-tests to assess the magnitude and significance of changes among program participants in the analytic sample for each outcome. For binary economic stability outcomes, we will descriptively report the percent of participants who opened a checking or savings account 1 year after enrollment, compared to the percent who had opened these accounts before the program. For binary employment outcomes, we will descriptively report the percent of participants who did not have a resume 1 year after enrollment, compared to the percent who did not have a resume before the program. We will adjust our p-values for multiple hypothesis testing and report the adjusted p-values in the appendix of the final report.

For the implementation analysis, program fidelity will be descriptively reported by the percentage of enrolled participants who receive: 1) any primary workshops, 2) employment supports, 3) substantive service contacts, 4) referrals. The program aims to provide all participants each of these four program components, so the percentage of participants who receive each of these will be compared to the 100% benchmark. Number of substantive service contacts per participant will also be compared to the benchmark of 8 SSCs set by OFA for FIRE grantees.

Exploratory analysis will examine how dosage varies by workshop characteristics (e.g., timing and length of sessions) and participant characteristics (e.g., age, employment status, relationship status).

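### Scoring fathers with no recent contact as Never lets a net change in contact alone move the R2 parenting-behavior mean, and the single pooled test cannot show that this has happened

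*SAP*

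**What the plan says.** R2 asks whether healthy parenting behaviors increase one year after enrollment (protocol, Evaluation Plan 1.1 and 1.2). The SAP scores this on a 1-to-5 frequency scale, from never to daily or nearly daily: "Average of 7 survey items that relate to frequency of positive interactions with" the father's youngest child (SAP, Defining analysis measures).

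On fathers without contact, the SAP's Outcomes text under Handling missing data reads: "Participants who have not seen their child within the past month will have their parenting behavior responses set to" the lowest category, scored 1. The same rule keeps these fathers in the R2 analysis rather than dropping them. No wave is named, so I read the rule as applying at entrance and at follow-up.

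The measure table gives a different sample for the same outcome: "Has at least one child age 24 or younger, saw child within past month". It names no wave either.

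On analysis, the SAP says: "We will use paired sample t-tests to assess the magnitude and significance of changes among program participants" (Analytic approach). It plans no breakdown by contact status, no analysis without the recoded scores, and no result for contact itself. Protocol section 9.1 lists hours with children and frequency of reaching out under parenting behavior, but the SAP composite keeps only the seven interaction items.

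On the population, the protocol says the program is not limited to fathers "housed in treatment facilities, non-custodial, or justice involved, the grantee (FAWIC) expects that many will have these characteristics" (Program Summary).

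**The concern.** Under the recode, a father who has not seen his child in the past month scores 1 on all seven items. If he is back in contact by the 1-year survey, his composite moves from the floor to whatever his in-contact level is. A father who loses contact moves the other way. The pooled mean change therefore combines two things: change in who has contact, and change in how often fathers in contact interact positively with the child.

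Some of the circumstances the protocol expects to be common can limit contact at entrance, and some can end within a year whatever the program does. If the no-contact share falls on balance, R2 can show a significant gain while fathers in contact at both waves have not changed. Protocol section 3 treats healthy behaviors as the primary outcomes that define the program's benefit, so a reader of the final report needs to know which component moved.

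**Working it through.** The documents give no sample size, standard deviation, effect size or significance level for R2, so there is no planned figure to reproduce. The program intends to serve 63 + 4 × 125 = 563 fathers, but that is not the number with both surveys. Everything marked as assumed below is illustration.

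**Mean change.** Let p0 be the share without contact at entrance, g the fraction of them who regain it, l the fraction of the others who lose it, and m the mean score when in contact, unchanged between waves. Then

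mean change = [p0·g − (1 − p0)·l] × (m − 1).

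The bracket is the net fall in the no-contact share. Take m = 3.5 (assumed), so m − 1 = 2.5.

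- Mild case, p0 = 0.20, g = 0.40, l = 0.05: (0.08 − 0.04) × 2.5 = **+0.10**.
- Stronger case, p0 = 0.30, g = 0.50, l = 0.05: (0.15 − 0.035) × 2.5 = **+0.2875**.
- Mild case with l = 0.10: (0.08 − 0.08) × 2.5 = **0**.

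**Test statistic.** Assume n = 150, SD of change 0.8 among fathers in contact at both waves, and a fixed 2.5-point shift for those who gain or lose contact.

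- Mild: E[x²] = 6.25 × 0.12 + 0.64 × 0.76 = 1.236; variance 1.236 − 0.010 = 1.226; SD 1.11; t = 0.10 / (1.11/√150) ≈ **1.1**.
- Stronger: E[x²] = 6.25 × 0.185 + 0.64 × 0.665 = 1.582; variance 1.582 − 0.083 = 1.499; SD 1.224; t = 0.2875 / (1.224/√150) ≈ **2.9**. Giving those who gain or lose contact the same 0.8 SD around their shift raises the SD to about 1.27, and t is still about 2.8.

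**Simulation.** 2,000 runs per row, with in-contact mean 3.5, SD 0.9, within-father correlation 0.6, scores limited to 1–5, two-sided 0.05 without multiplicity adjustment, and no true change given contact (all assumed). The last three columns give the chance of a significant gain.

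| No contact at entrance | Regain | Others lose | Mean change | N=100 | N=200 | N=300 |
|---|---|---|---|---|---|---|
| 10% | 50% | 0 | 0.125 | 25% | 46% | 64% |
| 20% | 50% | 0 | 0.25 | 67% | 92% | 98% |
| 20% | 50% | 5% | 0.15 | 24% | 43% | 59% |
| 30% | 50% | 0 | 0.375 | 92% | 99.8% | 100% |
| 20% | 50% | 12.5% | 0 | 2.2% | 2.8% | 2.5% |

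Among fathers in contact at both waves in the same simulated data, the rate was 1.8% to 3.3% across all scenarios run, against a nominal 2.5% in the upper tail.

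**Dependence on m.** A net fall of 10 percentage points gives 0.15 at m = 2.5, 0.25 at m = 3.5 and 0.35 at m = 4.5.

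**The case against.** Several counter-arguments have force.

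- *The outcome is interaction frequency.* For a father who has not seen his child all month, Never is close to the literal answer, and moving off it is a real change in the measure. The protocol also names father absenteeism as part of the problem. This stands: the recode is defensible, and a reader should not infer that a gain from regained contact is a gain without any change in parenting behavior. What remains is that the pooled number cannot say which component moved.
- *The rule cuts both ways.* This stands. A spurious-looking gain needs a net fall in the no-contact share; with 10% loss the mild case gives zero.
- *The population is less clear-cut than it may seem.* A reader might infer that most fathers enter confined and cut off from the child, so that an upward course is built in. The documents do not support that. The protocol lists non-custodial fathers along with the other two groups, gives no mix and no contact rate, and none of the three labels by itself means no contact in a month.
- *The design already concedes the missing counterfactual.* Protocol section 5 says so for R2, and section 1.2 labels R2 exploratory (section 3 calls the outcomes confirmatory). That caveat covers attribution to the program. It does not tell the reader whether contact or behavior given contact changed.
- *The measure table excludes no-contact fathers.* If that restriction governs at both waves, the problem disappears, at the price of selecting on follow-up contact. The point is therefore conditional on the floor-scoring rule prevailing.

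The SAP's planned multiplicity adjustment would lower the chance of a significant result somewhat, but it does not separate the two components.

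**Conclusion.** The point holds as a conditional one. If the floor-scoring rule governs, a net fall in the no-contact share can by itself produce a significant R2 gain, and the planned single test gives no means of seeing it. The size is the net fall times the distance from the floor to the usual in-contact score: +0.10 (not significant) to +0.29 (t about 2.9) in the two worked cases at an assumed 150 fathers, and zero when losses offset gains. All contact rates, the in-contact mean, the SDs and n are assumptions. The documents make a net fall plausible but do not establish it, so the claim is that this can happen, not that it will.

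**What to change.** First, reconcile the SAP's measure table with its Outcomes rule on who is in the R2 sample, and state the wave or waves at which past-month contact is judged.

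If the floor-scoring rule is kept, keep the pooled mean change as the main R2 result and add to Analytic approach:

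- (a) the percentage of fathers with past-month contact at entrance and at 1 year, with counts for contact at both, gained, lost and neither;
- (b) as a sensitivity result, the R2 mean change with a confidence interval among fathers with contact at both waves.

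Describe the pooled result as change in interaction frequency, including change in contact. Result (b) should not decide how the pooled result may be read. It selects on follow-up contact, which the program may affect, and a requirement that it merely move in the same direction would be met about half the time by chance when nothing had changed.

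The cost is one paragraph and one table, built from the contact item that the scoring rule already needs. The subgroup is smaller and selected, so it is to be read only beside the pooled mean. The gained and lost groups may also be small: in the mild case at 150 fathers, about 12 and 6, which is why only counts are asked for there. The SAP is dated January 2025, with follow-up planned to the end of May 2025 and the report due in September 2025, so on the documents' own timeline the change could precede the final analysis.

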9.3. METHODS OF DATA COLLECTION

If the evaluation will collect multiple waves of data, describe the timing of these waves below. When describing follow-up periods, specify whether the follow-up period will be post-baseline, post-random assignment, or post-program completion.

Wave of Data Collection (e.g., baseline, short-term follow-up, long-term follow-up)	Timing of Data Collection
Baseline	Collected immediately following informed consent and enrollment – during the orientation session or first workshop
Post-Test	Collected after the completion of core curriculum programming -during the last workshop session – approximately 4 weeks after enrollment.
1 year Follow-up (post-baseline)	Collected approximately one year after program enrollment/ baseline. Participants who did not complete the program will still be eligible for a follow-up survey as long as they consented to be in the study and took a baseline survey.

For each measure, describe how data will be collected detailing which data collection measures will be collected by which persons, and at what point in the programming or at what follow-up point.

Measure	Timing of Data Collection (baseline, wave of data collection)	Method of Data Collection	Who Is Responsible for Data Collection?	Impact Evaluations Only: Will Methods or Collection Procedures Differ by Study Group?	Administrative Data Only: Will data access require data sharing agreement?
Online Local Evaluation (OLLE) Baseline Survey	Baseline	Participant self-enters survey using online Qualtrics data collection platform	Case Manager and/or facilitator will proctor data collection and assist participants as necessary	N/A	N/A
nFORM Community Fathers Entrance Survey	Baseline	Participant self-enters survey using online nFORM data collection platform	Case Manager and/or facilitator will proctor data collection and assist participants as necessary	N/A	N/A
OLLE Post-Test Survey	Post-Test (approx. 4 weeks after enrollment)	Participant self-enters survey using online Qualtrics data collection platform	Case Manager and/or facilitator will proctor data collection and assist participants as necessary	N/A	N/A
nFORM Community Fathers Exit Survey	Post-Test (approx. 4 weeks after enrollment)	Participant self-enters survey using online nFORM data collection platform	Case Manager and/or facilitator will proctor data collection and assist participants as necessary	N/A	N/A

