9.4. ENSURING AND MONITORING DATA COLLECTION

Describe plans for training data collectors and for updating or retraining data collectors about procedures. Detail plans to regularly review data that have been submitted and to assess and swiftly address problems.

This evaluation will utilize both post-program surveys (completed at the completion of core programming) and follow-up surveys collected one year after enrollment / baseline. The methods for these data collections differ. The primary driver for post-program survey completion is high rates of program retention. This data point will be collected during the last workshop session – after (but during the same session of) the completion of the nFORM post-program data collection. As such only those individuals who complete the program and who are at the data collection session will participate in the post-program data collection. All program participants, even those who do not complete the program, will be sent a 1-year follow-up survey if they consent to be part of the evaluation and have taken a baseline survey.

All program staff and evaluation staff will undergo a rigorous set of trainings to prepare for the evaluation. All staff receive an overview and introductory training to present the goals and objectives of the evaluation effort and its importance to the overall project. Next, all staff receive training on human subject's protection and are required to pass a certification test on the subject matter. All staff will also receive a detailed training on the details of the evaluation including the evaluation tools, timing, and data collection process and the role and importance of data accuracy.

In addition, the data manager and the primary local evaluation staff will undergo a rigorous training process to better understand the context of HMRF research, training on data collection procedures they will be responsible for, and training on the nFORM system and use of nFORM data in a CQI process. MER is creating networks of CQI data managers and Evaluation Project Managers across the 12 projects that we are evaluating so that all staff have access to experienced data managers and evaluation staff who have done this work previously. This training takes the form of weekly training sessions that are currently under way.

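### The SAP scores any unlogged service as not received while acknowledging data-entry gaps, so fidelity against the 100% and 8-contact benchmarks can be understated by an amount the documents do not allow one to state

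*SAP*

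**What the plan says.** Under Handling missing data, Outcomes, the SAP makes three statements in succession.

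- An admission: "Data for the implementation outcomes could be missing as a result of programmatic data entry issues".
- An assumption, declared as made for this evaluation: "we assume that any primary or support services received by a participant are being accurately logged into nFORM".
- A scoring rule: "so a lack of documented attendance, service contacts, referrals, etc. is indicative of lack of services".

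Under Analytic approach, the SAP defines fidelity as "the percentage of enrolled participants who receive: 1) any primary workshops, 2) employment supports, 3) substantive service contacts, 4) referrals", and "the percentage of participants who receive each of these will be compared to the 100% benchmark". It adds: "Number of substantive service contacts per participant will also be compared to the benchmark of 8 SSCs set by OFA for FIRE grantees".

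The protocol fixes when the exit survey is taken. Section 9.3 places the post-test "during the last workshop session – approximately 4 weeks after enrollment". Section 9.4 says of the post-program survey: "This data point will be collected during the last workshop session", and limits it to fathers who finish the program and are present. Section 11.2 lists an nFORM client ID, name and date of birth as available for linking.

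Neither document plans a comparison of attendance logs with exit surveys, a sensitivity analysis for unlogged services, or an estimate of how often services go unlogged.

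**The concern.** The plan names a way in which service data can be missing and then treats every missing record as a true absence of service. Against a 100% benchmark, each unlogged service looks like a delivery failure, and the report cannot separate a records problem from a program problem.

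For the workshop component, the study will hold evidence that can contradict the rule. A father with an exit survey was, by the protocol's own procedure, in the last workshop session. If he has no logged attendance, the rule scores him as having received no workshop. If he consented and has an entrance survey, the SAP also puts him in the sample for the attitudinal outcomes. One report could then count him as a completer for R1, R4 and R6 and as unserved for I1 and I2.

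The exploratory dosage analysis concerns the same services. If logging quality differs between workshops, it could look like dosage that differs between workshops.

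**Working it through.** The documents give no logging-error rate, no number of workshop sessions and no expected fidelity figure, so there is no planned figure to reproduce. The rates below are assumptions used to show a range.

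**Inputs from the documents.** Benchmarks: 100% per component and 8 contacts per father (SAP, Analytic approach). Planned workshop numbers: 63 in year 1 and 125 in each of years 2-5 (Protocol, Program Summary), so 63 + 4 × 125 = 563, used only as a scale.

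**Assumed.** No over-logging; 1-10% of served fathers with no record at all; 10-30% of sessions unlogged; 4 or 8 sessions; 1-20% of contacts unlogged; gaps independent in steps 2 and 3.

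**Step 1. Whole record missing.** Reported receipt = true receipt × (1 − u), where u is the share of served fathers with no record for that component.

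- True receipt 100%: u = 1%, 5%, 10% gives 99%, 95%, 90%, or about 6, 28 and 56 of 563 fathers scored as unserved.
- True receipt 95%: u = 2%, 5%, 10% gives 0.95 × 0.98 = 93.1%, 0.95 × 0.95 = 90.3%, 0.95 × 0.90 = 85.5%.

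**Step 2. Scattered session gaps, any primary workshop.** A father who attended k sessions, each unlogged with probability m, is scored as unserved only if all k are unlogged: u = m^k.

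- k = 4, m = 10%: 0.0001, or 0.06 of 563 fathers.
- k = 4, m = 30%: 0.0081, or 4.6 fathers.
- k = 8, m = 30%: 0.00007, or 0.04 fathers.

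Scattered gaps therefore hardly move this measure. A material error needs whole attendance records to be missing.

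**Step 3. Service contacts, true count of 8.** Mean logged = 8(1 − m). Share of fathers still showing 8 = (1 − m)^8.

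| Contacts unlogged | Mean logged | Still at 8 |
|---|---|---|
| 1% | 7.92 | 92% |
| 5% | 7.60 | 66% |
| 10% | 7.20 | 43% |
| 20% | 6.40 | 17% |

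The percentage with at least one contact is barely touched here (1 − 0.2^8 = 0.999997 at 20% unlogged). The exposed figure is the count against 8.

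**Step 4. What the exit survey can show.** It is evidence of presence at one session, the last. It can reveal a completer whose attendance record is absent. It says nothing about earlier sessions, about fathers who left before the last session, or about employment supports, contacts and referrals.

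**The case against.** The best defence has four parts.

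First, the assumption is stated openly, so a reader of the report can allow for it. That is true, but the plan gives the reader nothing with which to judge it.

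Second, the protocol has safeguards. Its Evaluation Timeline schedules CQI meetings on service data and data cleanliness, section 6 has the CQI Team review nFORM data for problems, and section 9.4 provides bi-weekly downloads and staff training on data accuracy. These may well keep gaps small. They do not change the scoring rule or require remaining gaps to be reported.

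Third, the workshop measure is robust to scattered gaps, as step 2 shows. This stands, and it limits the concern to missing whole records for that component.

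Fourth, the outcome questions are untouched. This also stands: the R1-R7 samples are defined by consent and surveys, and the change scores use survey answers only.

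Stronger readings are tempting but not supported. A reader might infer that fidelity is in fact understated, or that the study already holds records disproving the assumption. The SAP says only that data could be missing, and no discordant record or error rate appears in either document. A reader might also take incomplete logged attendance among fathers with an exit survey as a logging-error rate. The documents do not say that completion requires every session, so a gap at an earlier session may be a true absence. Finally, calling the logged figures a lower bound without qualification would assume that nothing is over-logged or credited to the wrong father, which the documents do not establish.

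**Conclusion.** The concern holds in a limited form. The rule treats an acknowledged missing-data mechanism as if it did not operate, and no check is planned although one is available. If services go unlogged and over-logging is negligible, fidelity can only be understated. The amount cannot be derived from the documents.

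Workshop receipt falls one-for-one with the share of served fathers whose whole attendance record is missing and is nearly immune to scattered gaps. The contact count is the sensitive figure, and the exit survey cannot correct it. The step 2 and 3 figures also rest on independent gaps and, for contacts, on a true count of 8; clustered gaps would give different values.

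The consequence is confined to what I1 and I2 can conclude against the benchmarks and to the exploratory dosage analysis. It does not threaten the study's outcome results, but it is worth correcting because the check is cheap.

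**What to change.** Amend the SAP text on missing implementation data as follows.

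1. Link nFORM attendance to exit surveys by client ID. Report receipt of any primary workshop twice: as logged, and after counting each father with an exit survey as having received at least one workshop. State that the second figure corrects completers only, so unlogged attendance among non-completers remains, and that it relies on exit surveys having been taken in the last session as the protocol describes.
2. Report two counts among fathers with an exit survey: those with no logged attendance for the last session, and those with no logged attendance at all. Present these as the observed discordance. Do not count missed earlier sessions as logging errors.
3. Label the employment-support, service-contact and referral figures as documented receipt when comparing them with 100% or with 8, and say that they are a lower bound only if there is no over-logging.

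The cost is a few lines of SAP wording, one cross-check and two reported counts. The protocol lists both the exit survey and the linking identifiers under nFORM, and the SAP places the service logs there too, so no new data collection is needed.
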